8.2. Trial supplies and incoming quality check

- A list of materials for Truenat MTB and RIF testing is provided in Appendix 1.
- Income Quality Check (IQC) procedures are described in the Manual of Procedures. This will be conducted upon arrival of each new shipment of assays. New lots may only be used after this quality check is successfully passed.

8.3. Other Trial Procedures

8.3.1. Assessment of patient important outcomes

The following will be assessed as patient important outcomes using the Truenat MTB assays and RIF assay compared to routine tests

- Time to detection of TB and susceptibility to RIF.
- Yield over smear microscopy and Xpert MTB/RIF.
- Upfront diagnosis of RIF (reflex on all Truenat MTB or MTB Plus positive versus current standard of smear-positive reflexed to Xpert MTB/RIF based on risk factors).

See Patient important outcomes under Statistical analysis plan.

8.3.2. Participant follow-up

A follow-up visit at Day 56 (+/- 14 days) post-enrolment will be conducted to a subset of participants in order to collect additional information on the TB status.

- **Culture-negative, Truenat MTB (and/or MTB plus) and Xpert discordant cases.** During the prospective assessment, Truenat results will not be provided to clinicians or participants or used for

decision-making. Thus participants who are Xpert-negative but Truenat-positive at enrolment (“discordant”) will not be treated on the basis of Truenat results. All culture negative cases with discrepant Truenat and Xpert results will undergo a follow-up visit performed at Day 56 (+/-14) post-enrolment to assess:

- Interval medication history, including TB treatment and clinical evolution.
- An additional spot sputum will be obtained for smear microscopy and culture (LJ and MGIT) provided the patient was not started on therapy and is able to provide a spontaneously produced sputum sample.

This will aid in the identification of patients who would be diagnosed (in the absence of Truenat MTB assays being available for decision making) on clinical grounds.

- **Cases Detection group with negative results.** The first 267 patients who are negative on all tests (approximately 20%) will be followed at Day 56 (+/-14) post-enrolment to assess:
 - Interval medication history, including TB treatment and clinical evolution
 - An additional spot sputum will be obtained for smear microscopy and culture (LJ and MGIT) provided the pulmonary symptoms persist and the patient was not started on therapy

The purpose of this follow-up visit is to identify the participants in this subset who are diagnosed/initiated on treatment on clinical grounds and those that are missed completely.

A follow-up visit is not required for participants who are started on treatment (based on Xpert or culture results).

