Eligibility criteria	
Individuals who have symptoms consistent with pulmonary TB presenting to participating centres will be assessed and asked to participate. Participants will be categorised into 2 groups:
 
Case Detection group - Only participants who have not received any form of TB treatment within the prior 60 days will be enrolled.
 
Drug Resistant group – Non-converting TB cases presumed to be at risk of drug-resistance.

Primary outcomes	
1. Primary outcomes
 
1.1. Sensitivity of the Truenat MTB assays (including analysis by smear-status and by sample).
 
1.2. Specificity of the Truenat MTB assays (including analysis by sample).
 
1.3. Sensitivity of the Truenat MTB-RIF Dx assay.
 
1.4. Specificity of the Truenat MTB-RIF Dx assay.

Secondary outcomes	
2. Secondary outcomes
 
2.1. Sensitivity of the Truenat MTB assays and MTB-RIF Dx assay compared to Xpert MTB/RIF.
 
2.2. Specificity of the Truenat MTB assays and MTB-RIF Dx assay compared to Xpert MTB/RIF.
 
2.3. Patient important outcomes (see details in section Patient important outcomes under Statistical analysis plan).

Trial duration	Approximately 12 months
Time schedule	Trial start expected Q4-2018 with enrolment completion by Q2-2019. Follow-up after 2 months and testing of discordant cases completed Q4-2019.
GCP statement	All studies sponsored by FIND will be conducted in accordance with ICH-GCP Guidelines (ICH-GCP E6 R2), to the extent possible in the research setting as well as all national legal and regulatory requirements (as apply).

Schedule of Activities

Procedure	Enrolment		Follow-up visit 1	Notes
	Day 1	Day 2	Day 56 (±14)	
Informed consent	X			
Inclusion and exclusion criteria	X			
Demography	X			
Medical history (includes prior history of TB)	X			
Sputum sample collection	X	X*		
Blood sample collection (optional)	X			HIV testing will be offered to all participants as part of the trial procedures, unless a prior result is available (see Section 8)
AE/SAE review	←=====→			
Assess interval medication history			X	
 • Culture-negative, Truenat MTB (and/or MTB plus) and Xpert discordant cases. • 20% of Case Detection Group participants with negative results for all test, including culture

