Spot sputum (microscopy and culture)			X [#]	
 • Culture-negative, Truenat MTB (and/or MTB plus) and Xpert discordant cases. • 20% of Case Detection Group participants with negative culture

* Two sputum samples are collected on both Day 1 and Day 2. On Day 1, two spot sputa are collected. On Day 2, firstly, a morning sputum is self-collected in a pot taken home on Day 1. Secondly, an additional sputum is collected when the participant returns to the clinic to deliver the sputum pot from home.

[#] An additional spot sputum will be obtained at follow-up for smear microscopy and culture if i) not on TB treatment and ii) sputum can be produced spontaneously.

1 Introduction

The Truenat MTB, MTB plus and MTB-RIF Dx assays are a set of new tests developed for the diagnosis of tuberculosis (TB) and detection of resistance to rifampicin (RIF), a commonly used drug for treatment of active TB.

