10.2. Sample Size Determination

The sample size was chosen to achieve high confidence in the accuracy estimates for MTB-detection and RIF resistance detection for the overall multi-country trial for which the Indian trial is one of the countries.

Based on an expected sensitivity of Truenat MTB plus for detection of TB among smear-negative/culture-positive cases of 67% (based on preliminary data), 80 smear-negative/culture-positive cases would be required to achieve a total width of the 95% confidence interval of 20% (95%CI: 57 to 77). Assuming a TB prevalence of 20% and a prevalence of smear-negative/culture-positive cases among TB cases of 30%, the total number of subjects to be enrolled would be 1,333. To account for losses, this is inflated by 20%, yielding a final sample size of 1,666 participants under investigation for TB overall.

In India, two thirds of these trial participants will be recruited i.e. $n = 1,110$ thus 67 smear-negative/culture-positive cases and a 95% confidence interval of 21% could be achieved (95%CI 55 to 79).

The other one-third of enrolled participants ($n = 556$) will be recruited in three other countries in order to provide geographic variation.

The secondary objective of determining diagnostic accuracy of RIF resistance by Truenat MTB is based upon an expected Truenat RIF sensitivity of 95% with a confidence interval of 10% (90-100%), requiring $n=37$ RIF-resistant participants detected. Assuming a prevalence of 20% culture-positive TB cases detected across all presumed TB cases, and 2.8% RIF resistance amongst all culture-positive TB cases and 12% prevalence of RIF resistance amongst TB retreatment cases, we predict 1,542 re-treatment patients would thus need to be enrolled. While the prevalence of culture-positive TB cases may be higher if enrolment is conducted at a drug-resistance TB referral clinic, we conservatively accept that this may not be the case. As such, we may not reach sufficient sample size to allow analysis of secondary objectives in this trial. Detection of RIF resistance will be continually monitored throughout the trial, and any possible shortfall will be supplemented with a future sub-study, if needed, using confirmed RIF-resistant sputum samples from the FIND specimen bank of cryopreserved samples. We will place an enrolment cap of 200 enrolled participants in the drug resistance group for the entire trial, in order to not undermine the primary objective of enrolment of smear-negative culture

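### Following the first 267 all-negative participants limits the Day 56 subset to the early part of enrolment, and the Schedule of Activities and section 8.3.2 disagree on follow-up sputum

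*Protocol*

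**What the plan says.** Section 8.3.2 of the protocol plans a Day 56 (±14) visit for two subsets. The first is culture-negative participants whose Truenat and Xpert results disagree. The second comes from the Case Detection group: "The first 267 patients who are negative on all tests (approximately 20%) will be followed" at that visit. No allocation by site, period or chance is described. The stated aim of the second subset is to "identify the participants in this subset who are diagnosed/initiated on treatment on clinical grounds and those that are missed completely". Follow-up sputum in it is taken "provided the pulmonary symptoms persist and the patient was not started on therapy".

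The Schedule of Activities describes the same visit differently. Its medication-history row names "20% of Case Detection Group participants with negative results for all test, including culture". Its spot-sputum row names "20% of Case Detection Group participants with negative culture". Its footnote allows the sputum "if i) not on TB treatment and ii) sputum can be produced spontaneously". Section 7 makes adherence to the Schedule mandatory, so both texts bind the sites.

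**The concern.** A subset meant to show what happens to participants whom every test called negative should reflect the participants it stands for. Taking the first ones to arrive closes selection once the places are full. Anyone enrolled afterwards has no chance of a visit, and a site that opens late may contribute nobody. Clinical practice in starting treatment without a positive test may vary by site and over time. If it does, the proportions treated on clinical grounds or missed would not carry over to the unfollowed all-negatives.

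The second issue is separate. Two sites can follow the protocol correctly, one from section 8.3.2 and one from the Schedule, and collect follow-up sputum from different people under different conditions. That changes who can be found to have been missed.

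**Working it through.** **Inputs.** Subset size 267 and the label of about 20% (section 8.3.2). Evaluable number: "the total number of subjects to be enrolled would be 1,333" (section 10.2). Enrolled number: "this is inflated by 20%, yielding a final sample size of 1,666 participants under investigation for TB overall" (section 10.2). TB prevalence 20% and a Drug Resistant cap of 200 (section 10.2). Enrolment period 32 weeks (section 14).

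**The plan's own figure.** 0.20 × 1,333 = 266.6, so 267. Equally, expected culture-negatives among all enrolled are 0.80 × 1,666 = 1,332.8, and 20% of that is also 266.6. The figure reproduces.

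**Weeks to fill, even accrual.** The protocol gives no share negative on every test. 80% is the culture-negative share implied by 20% prevalence, and some culture-negatives will be positive on another test. I therefore take a share *s* of those enrolled from 60% to 80%. *N* is 1,666 (all enrolled) or 1,666 − 200 = 1,466 (Case Detection only, if the cap fills). Weeks = 267 / (*N* × *s* / 32). For example, 267 / (1,666 × 0.80 / 32) = 267 / 41.65 = 6.4.

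| Share *s* | *N* = 1,666 | *N* = 1,466 |
|---|---|---|
| 80% | 6.4 weeks (20% of enrolment) | 7.3 (23%) |
| 70% | 7.3 (23%) | 8.3 (26%) |
| 60% | 8.5 (27%) | 9.7 (30%) |

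Taking 80% negative and 20% losses in the Case Detection group gives 267 / (0.80 × 0.80 × 1,466 / 32) = 9.1 weeks (28%), inside this range.

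**Weeks to fill, linear ramp-up from zero (assumed).** Cumulative all-negatives at week *t* are *N* × *s* × (*t*/32)², so *t* = 32 × √(267 / (*N* × *s*)). At *s* = 80% this gives 14.3 weeks (*N* = 1,666) and 15.3 (*N* = 1,466). At *s* = 60% it gives 16.5 and 17.6. The range is about 45% to 55% of enrolment.

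**What one in five yields.** Case Detection negatives if the cap fills: 0.80 × 1,466 = 1,172.8. One in five is 234.6, about 235. After 20% losses it is 0.80 × 234.6 = 187.7, about 188. Keeping 267 would need 267 / 1,172.8 = 23% before losses, or 267 / (0.80 × 1,172.8) = 28% after.

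**The sputum texts side by side.**

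| | Section 8.3.2 | Schedule of Activities |
|---|---|---|
| Who gives sputum | Negative on all tests | Negative culture |
| Condition besides no treatment | Persisting pulmonary symptoms | Spontaneous sputum |

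A culture-negative participant with another positive test falls in the Schedule's sputum row but not in 8.3.2's all-negative group. A symptom-free participant who can still produce sputum qualifies under the footnote but not under 8.3.2.

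**The case against.** The subset is descriptive. Section 8.3.2 speaks of identifying participants within it. No proportion missed appears among the endpoints, the patient-important outcomes or the listed analyses. That stands: the criticism applies to any proportion drawn from the subset, not to a planned estimator.

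Four stronger readings might be inferred, and the documents do not support them.

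- *That this is the only check on false-negative culture.* Section 8.3.3 also re-examines discordant cases and an equal number of concordant ones, and the reference standard already uses two MGIT and two LJ cultures.
- *That high-volume centres will be over-represented.* The 40, 120 and 300 per month in Table 2 are routine volumes at Indian centres, not trial accrual. A one-in-five sample within each site is also proportional to volume: with one site of each type, the mix is 9%, 26% and 65% either way. What remains is calendar time and staggered opening. Site start dates are not given. The protocol history entry of 28 December 2018 shows ethics approval pending at two institutions, so staggering is plausible but its extent is unknown.
- *That the subset covers at most the first quarter of enrolment.* This holds only in the faster even-accrual cases.
- *That specificity is distorted because the Non-TB definition depends on treatment status.* Any one-in-five sample leaves about 80% of all-negatives without a Day 56 visit, so the selection rule does not create that gap.

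On sputum, it can be said that the two conditions are compatible and that negative culture is shorthand for the row above it. A participant can meet both conditions, but can also meet only one. The shorthand reading is possible, but sites should not have to guess. No material shift in a result has been shown.

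**Conclusion.** The concern holds as a modest design weakness plus a textual conflict. Selection closes well before enrolment ends in every scenario examined: after about 6 to 10 of 32 weeks under even accrual with a 60-80% all-negative share, or about 14 to 18 weeks under a linear ramp-up. The shares and the ramp-up are assumptions; the 267, 1,666, 200 and 32 weeks are the protocol's. The proportions treated clinically or missed will describe early enrolment only. The direction and size of any resulting bias cannot be derived from the documents. Primary sensitivity against culture is unaffected, and the number 267 is not an error. The disagreement between section 8.3.2 and the Schedule of Activities is plain on the text and does not depend on how the subset is chosen.

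**What to change.** In section 8.3.2, replace the first-come rule with a systematic sample of Case Detection all-negatives within each site, from a random start and at a fixed fraction of about one in five, over the whole enrolment period. Count in order of enrolment, since Table 4 makes an LJ culture negative only after more than 56 days. State whether the fraction or the total is binding: one in five gives about 235 visits before losses and about 188 after them if the Drug Resistant cap fills, whereas holding 267 means a fraction of about 23% to 28%. Carry the same rule into the Schedule of Activities.

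Separately, the sponsor must reconcile section 8.3.2 with the Schedule's sputum row and footnote, so that one wording states who gives follow-up sputum and on what condition. Which condition is right is the sponsor's decision.

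The cost is protocol text and selection tracking at each site throughout enrolment. The number of visits stays about the same or falls somewhat, depending on which figure is made binding.

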8.3.3. Analysis of discordant results

Given that the sensitivity and specificity of culture and culture-based DST for Rifampicin is not perfect, misclassification of samples by these reference standards may introduce bias into the sensitivity and specificity estimates for the Truenat assays and underestimate their diagnostic performance.

In order to address this bias, cases with discordant results (and a subset of cases with concordant results) will be further assessed following a Manual of Procedures and described separately in the final trial report. The same number of non-discardant cases will be tested to avoid introduction of additional bias.

8.4. Genetics

Besides sequencing of *M. tuberculosis* to identify mutations recognized to be associated with drug resistance, no other genetic tests are evaluated in this trial.

8.5. Biomarkers

Biomarkers are not evaluated in this trial.

9. Safety and Incident Reporting

Given the nature of this trial i.e. diagnostic accuracy and comparison of diagnostic solutions, the probability of an AE and SAE to be associated with the investigational products is exceedingly rare.

Safety reporting is therefore limited in scope to events associated with the collection of samples and those that occur at participating laboratories using the investigational medical device i.e. TruePrep Auto and Truenat UnoDx. For the purposes of this trial only fatal SAEs and medical device incidents fulfilling the definition of AE or SAE (see section 9.2 Medical Device Incidents) will be reported.

The definitions can be found in Appendices 2 and 3.

The investigator and any qualified designees are responsible for detecting, documenting, and recording events that meet the definition of an AE or SAE and remain responsible for following up all AEs that are serious, considered related to the trial intervention or trial procedures, or that caused the participant to discontinue the trial. If the AE meets the definition of a SAE it must be reported to FIND regardless if associated with and of the investigational diagnostic devices.

9.1. Time Period for Collecting SAE Information

Relevant AE or SAEs will be collected from the signing of the informed consent form (ICF) until the follow-up visit.

Fatal SAEs will be recorded and reported to FIND or designee within 24 hours, as indicated in Appendix 2. The investigator will submit any updated SAE data to FIND within 24 hours of it being available.

Investigators are not obligated to actively seek SAEs after conclusion of the trial participation.

The method of recording, evaluating, and assessing causality of the SAE and the procedures for completing and transmitting SAE reports are provided in Appendix 2.

9.1.1. Reporting and Follow up of SAEs

Further information on follow-up procedures is given in Appendix 2.

9.1.2. Regulatory Reporting Requirements for SAEs

- Prompt notification by the investigator to FIND of a fatal SAE is essential so that legal obligations and ethical responsibilities towards the safety of participants and investigational medical device operators are met.
- FIND has a legal responsibility to notify both the local regulatory authority and other regulatory agencies about the safety of a trial intervention under clinical investigation. FIND will comply with country-specific regulatory requirements relating to safety reporting to the regulatory authority, Institutional Review Boards (IRB)/Independent Ethics Committees (IEC), and investigators.
- An investigator who receives an investigator safety report describing a fatal SAE or other specific safety information (e.g. summary or listing of SAEs) from FIND will review and then file it in the ISF and will notify the IRB/IEC, if appropriate according to local requirements.

9.2. Medical Device Incidents (including Malfunctions)

Medical devices are being provided for use in this trial for the purpose of evaluating diagnosis of TB and detecting RIF resistance. In order to fulfil regulatory reporting obligations worldwide, the investigator is responsible for the detection and documentation of events meeting the definitions of incident or malfunction that occur during the trial with such devices.

The definition of a Medical Device Incident can be found in Appendix 3.

NOTE: Incidents fulfilling the definition of an AE/SAE (e.g. any event that occurs as a result of insufficient or inadequate instructions for use, installation, or operation, or any malfunction of the investigational device, as well as any event resulting from operator error(s), intentional misuse of the investigational medical device or protocol violation) will follow the processes outlined above and in Appendix 3 of the protocol.

9.2.1. Time Period for Detecting Medical Device Incidents

Medical device incidents or malfunctions of the device that result in an incident will be detected, documented, and reported during all periods of the trial in which the medical device is used.

Medical device incidents meeting the definition of AE or SAE will be reported to FIND or designee within 24 hours, as indicated in Appendix 3. The investigator will submit any updated SAE data to FIND within 24 hours of it being available.

If the investigator learns of any incident at any time after a participant has been discharged from the trial, and such incident is considered reasonably related to a medical device provided for the trial, the investigator will promptly notify FIND.

The method of documenting Medical Device Incidents is provided in Appendix 3.

9.2.2. Follow-up of Medical Device Incidents

- All medical device incidents involving an AE will be followed and reported in the same manner as other AEs (see Appendix 2). This applies to all participants, including those who discontinue trial intervention as well as medical device operators.
- The investigator is responsible for ensuring that follow-up includes any supplemental investigations as indicated to elucidate the nature and/or causality of the incident.
- New or updated information will be recorded on the originally completed form with all changes signed and dated by the investigator.

9.2.3. Reporting of Medical Device Incidents to Sponsor

- Medical device incidents will be reported to FIND within 24 hours after the investigator determines that the event meets the protocol definition of a medical device incident.
- The Medical Device Incident Report Form will be sent to FIND by email.
- The same individual will be the contact for the receipt of medical device reports and SAE.

9.2.4. Regulatory Reporting Requirements for Medical Device Incidents

- The investigator will promptly report all incidents occurring with any medical device provided for use in the trial in order for FIND to fulfil the legal responsibility to notify appropriate regulatory authorities and other entities about certain safety information relating to medical devices being used in clinical studies.
- The investigator, or responsible person according to local requirements (e.g. the head of the medical institution), will comply with the applicable local regulatory requirements relating to the reporting of incidents to the IRB/IEC.

10. Statistical Considerations

This trial is designed to assess diagnostic accuracy of the index test compared to culture reference standard, and to assess the diagnostic accuracy of RIF resistance detection compared to a reference standard of phenotypic drug susceptibility testing. Further this trial will compare diagnostic accuracy and RIF detection of the index tests to that of Xpert MTB/RIF. As such, the trial has been designed to capture a sufficient number of smear negative TB cases to be able to provide estimates of sensitivity with a confidence interval width of approximately 20%.

This section provides an overview of the data analysis strategy and methodology. A detailed Statistical Analysis Plan (SAP) will be written before the start of recruitment.

